7.1 Schedule of Assessments

The study consists of a 7-day inpatients screening phase (up to a 7-day extension of the screening phase is allowed, if necessary with the approval of the Medical Monitor), Study Treatment Period (Days 1 to Day 28 including Baseline [Day 1]), Stabilization Period (up to 5 days, Days 29 to 33), and EoS Visit (Visit 7 [Day 42] ± 2 days). Therefore, the maximal study duration for an individual patient will be approximately up to 8 weeks.

Note, this is an inpatient study from Screening to the end of the Stabilization Period. The procedures to be performed throughout the study are outlined in the SoA (Table).

Confidential Page 53 of 102

Table do: Schedule of Assessments

Event	Screening Phase	Baseline	Study Treatment Period								End of Stabilization Period	End of Study Visit
Event	Up to 7 days ^a	Day 1	Days 2-7	Day 8 ±1	8 9-14	Day 15 ±1	Days 16-20	Day 21 ± 1	Days 22-27	Day 28 or ET	33°	Day 42± 2
Visit Number	1	2	NA ^b	3	NA ^b	4	NA ^b	5	NA ^b	6	7	8
Entrance/Screening Criteria												
Informed Consenta	X											
Admission to Inpatient Unit ^a	X											
Inclusion/Exclusion Criteria Review ^a	X	X										
Screening Adjudication Form(s) and Recordings ^d	X											
Medical History ^e	X											
MINI-Plus BPD 7.0.2	X											
Prior Medication Washout ^f	X											
Hepatitis/HIV	X											
Urine Drug and Blood Alcohol Screen ^g	X ^g											
Randomization		X										
Efficacy												
(PCRS) SCI-PANSS and CGI-S	X ^h	X ^h		X		X		X		Xh		
Cogstate Test	X^{i}	Xi								Xi		
Safety												
Prior and Concomitant Medication	X	X	X	X	X	X	X	X	X	X	X	X
Physical Exam ^j	X	X		X		X		X		X		X
AIMS	X	X^k		X^k		X^k		X^k		X^k		
SAS	X	X^k		X^k		X^k		X^k	_	X^k		
BARS	X	X^k		X^k		X^k		X^k		X^k		
C-SSRS	X ^l	X ^m		X ^m		X ^m		X ^m		X ^m	X ^m	X ^m
BMI and Waist Circumference ⁿ	X	X		X		X		X		X		

Page 54 of 102

	Screening Phase	Baseline Day 1	Study Treatment Period								End of Stabilization Period	End of Study Visit
Event	Up to 7 days ^a		Days 2-7	Day 8 ± 1	Days 9-14	Day 15 ± 1	Days 16-20	Day 21 ± 1	Days 22-27	Day 28 or ET	33°	Day 42± 2
Visit Number	1	2	NAb	3	NAb	4	NAb	5	NA ^b	6	7	8
Urine Pregnancy Test ^o	X	X								X	X	
Clinical Laboratories (for Screening and exclusionary purposes) ^p	X											
Hematology, Serum Chemistry including Prolactin, Urinalysis ^q	X	X		X		X		X		X		
TSH ^r	X									X		
PT, aPTT, and INR	X	X								X		
ACTH and Cortisol		X								X		
Resting 12-lead ECG ^s	X	X		X		X		X		X		

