7.2.10 Visit 6 (Study Day 28)

On Study Day 28, all assessments should be performed on the same day; the last day of study drug dosing is Day 28 and, if possible, when any patient discontinues prior to this visit, the following assessments will be performed:

• Recording of concomitant medications (e.g., prescription and nonprescription medications)

Confidential Page 62 of 102

- Full physical examination (if applicable)
- Bodyweight, BMI (derived programmatically from body weight and height measurements), and waist circumference
- Vital signs
- Resting 12-lead ECG (triplicate, further information in Section 8.2.3)
- Collection of blood and urine samples for clinical laboratory tests. Additional information is presented in the footnotes to the SoA (Table)
- Study drug administration
- Urine pregnancy test for all females of childbearing potential
- Assessment and recording of AEs
- PANSS. PCRS must be administered before PANSS
- CGI-S
- C-SSRS
- AIMS, 3 to 6 hours post-dose
- BARS, 3 to 6 hours post-dose
- SAS, 3 to 6 hours post-dose
- Cogstate test

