8.2.5 Adverse Events

All AEs occurring after the patient signs the ICF and up to 14 days after the end of the Treatment Period will be recorded.

See Section 9 for additional information.

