10.4.5.2 Adverse Events

AEs will be characterized by type, severity, seriousness, and relationship to treatment. AEs will be coded by preferred term and system organ class (SOC) using Medical Dictionary for Regulatory Activities (MedDRA) Version 23.0.

The incidence of TEAEs (number and percent of patients reporting the AE at least once during the study), SAEs, AEs related to study treatment, SAEs related to treatment, and AEs leading to study discontinuation will be summarized by treatment.

A TEAE is defined as any AE that has an onset on or after the dose of study drug, or any pre-existing condition that has worsened on or after the first dose of study drug.

Confidential Page 84 of 102

Any AE commencing after the last dose of study drug plus 14 calendar days will not be considered treatment-emergent.

The incidence of TEAEs and treatment-related AEs will also be summarized by maximum severity and strongest relationship to study drug by MedDRA primary SOC and preferred term. The summary will include the total number and percentage of patients reporting a particular event as well as the total number of events. In counting the number of events reported, a continuous event, i.e., reported more than once and which did not cease, will be counted only once; noncontinuous AEs reported several times by the same patient will be counted as multiple events.

Relative risks for the occurrence of any AE (i.e., at least 1 AE) during the course of the study as well as for each SOC/preferred term will be calculated for each LB-102 dose vs placebo alongside 95% CI and *P* values. For such analysis, a Poisson regression model with a log-link and a robust error variance will be considered, using the binary indicator for the presence of a given SOC/preferred term (or any AE) as response and treatment as the only covariate whose betas will be exponentiated to return the associated relative risk.

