### **5.2.5 Duration / Study Day / Time**

Study day will be calculated as the number of days from first dose of study drug.

- date of event – date of first dose of study drug + 1, for events on or after first dose
- date of event – date of first dose of study drug, for events before first dose

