### 5.13.1 Adverse Events

Treatment-emergent adverse events (TEAEs) are reported according to protocol as any AE that has an onset on or after the dose of study drug or any pre-existing condition that has worsened on or after the first dose of study drug through 14 days following last dose of study drug. The following TEAE flag will be applied to distinguish AEs from TEAEs:

- Any AE that has a start date and time on or after the first dose of study drug and before last dose of study drug + 14 days

A treatment-related AE is defined as an AE as being possibly related or related to the study drug. If an AE has missing relationship it is assumed to be related to the study drug for analysis purposes.

Maximum severity will be assumed for an AE with missing severity.

The following tables will be presented for AEs incidence and/or number of events will be reported as appropriate:

- Overall summary of AEs:
  - TEAEs
  - Treatment-related TEAEs
  - Treatment-emergent serious adverse events (TESAEs)
  - Treatment-related TESAEs
  - TEAEs by severity
  - TEAEs leading to study discontinuation
  - Deaths
- TEAEs by system organ class and preferred term
- Treatment related TEAEs by system organ class and preferred term
- TESAEs by system organ class and preferred term
- TEAEs by system organ class, preferred term and maximum severity
- TEAEs by system organ class, preferred term and strongest relationship
- TEAEs leading to study discontinuation by system organ class and preferred term
- Listing of Serious AEs.
- Listing of Deaths.

Adverse event incidence is counted only once per system organ class and once per preferred term. The number and percent of patients experiencing events are reported. Outputs reported at maximum severity or strongest relationship show the highest severity/relationship reported by a patient per system organ class and preferred term.

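### The SAP's treatment-emergent flag stops short of day +14 after the last dose, a day that the protocol and the SAP's own definition include

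*SAP*

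**What the plan says.** Three statements set the end of the treatment-emergent window.

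- Protocol Section 10.4.5.2: "Any AE commencing after the last dose of study drug plus 14 calendar days will not be considered treatment-emergent".
- SAP Section 5.13.1, definition sentence, which presents itself as following the protocol: the window runs "through 14 days following last dose of study drug".
- SAP Section 5.13.1, the flag that follows. Its lower bound reads "Any AE that has a start date and time on or after the first dose of study drug"; its upper bound reads "and before last dose of study drug + 14 days".

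The surrounding calendar is as follows. In Protocol Section 7.2.10, "the last day of study drug dosing is Day 28". Protocol Section 7.1 schedules the "EoS Visit (Visit 7 [Day 42] ± 2 days" (the schedule table and Section 7.2.13 number this Visit 8; the day is the same). Protocol Section 8.2.5 states: "All AEs occurring after the patient signs the ICF and up to 14 days after the end of the Treatment Period will be recorded". SAP Section 8 declares a change of regression model for adverse events but no change to the TEAE window.

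**The concern.** The first two statements include day +14; the flag does not. The flag is the statement a programmer would most naturally code, and it is the one that departs from the protocol. It can therefore remove from the TEAE tables events that the protocol both collects and counts.

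The tables that depend on it are the overall TEAE summary and the tables by system organ class and preferred term, including related, serious, severity and relationship. SAP Section 10 plans independent programming for most of these. Two programmers could each follow a different sentence of Section 5.13.1 and obtain different counts, with nothing in the SAP to say which is right.

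**Working it through.** **Inputs**

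- First dose is Day 1. SAP Section 5.2.5 computes study day as event date minus "date of first dose of study drug + 1, for events on or after first dose".
- Last dose for a completer is Day 28 (Protocol Section 7.2.10).
- End of Study is Day 42 ± 2, so Days 40 to 44 (Protocol Section 7.1).
- The clock time of dosing is not given. Protocol Section 8.3 refers only to a morning dose, so 07:00 to 12:00 is taken as an assumed range.

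**Step 1: the boundary day.** 28 + 14 = Day 42, which reproduces the protocol's nominal End of Study day.

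**Step 2: classify onsets in a completer under three rules.**

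- (a) Protocol: onset date ≤ last-dose date + 14.
- (b) SAP flag, dates compared: onset date < last-dose date + 14.
- (c) SAP flag, dates and times compared: onset date-time < last-dose date-time + 14 × 24 h.

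| Onset | (a) Protocol | (b) Flag, dates | (c) Flag, dates and times |
|---|---|---|---|
| Up to Day 41 | TEAE | TEAE | TEAE |
| Day 42, before the clock time of the last dose | TEAE | not | TEAE |
| Day 42, at or after that clock time | TEAE | not | not |
| Day 43 or later | not | not | not |

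The rules differ on Day 42 only.

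**Step 3: size under (b).** The window is Days 1 to 42 under the protocol and Days 1 to 41 under the flag. The loss is 1/42 = 2.4% of window days, or 1/14 = 7.1% of the post-dose days 29 to 42.

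**Step 4: size under (c).** The share of Day 42 lost is (24 − h)/24, where h is the clock hour of the Day 28 dose:

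- h = 7: 17/24 = 70.8%
- h = 9: 15/24 = 62.5%
- h = 12: 12/24 = 50.0%

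**Step 5: early terminators.** For a last dose on Day d, the boundary is Day d + 14 and the same comparison applies. They lose all or part of that day.

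**Step 6: which of (b) or (c) applies.** The flag names date and time, which points to (c). The documents do not say whether AE onset time is collected. SAP Section 5.2.6 imputes missing and partial dates but gives no rule for times, so (b) is a plausible implementation that is not stated.

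**The case against.** The case for leaving this alone has several parts.

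- **It may be only wording.** If the definition sentence is read as elapsed time, the two SAP sentences differ by a single instant. But that sentence claims to follow the protocol, and the protocol counts calendar days. On calendar days the flag is short under either comparison.
- **The events matter little.** Standard antipsychotic treatment is to start on Day 29 (schedule of assessments, note w), and Protocol Section 7.2.12 expects plasma concentration to be minimal within 5 days of the end of treatment. A Day 42 onset therefore comes after the end of dosing and, for most patients, on another antipsychotic. The same rule applies to every arm, so no bias in a given direction is shown. This stands, and it lowers the importance.
- **Nothing is lost from view.** All AEs are listed, and deaths and serious AEs have their own listings. This also stands.

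A reader might infer more than the documents support:

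- *That every Day 42 onset is dropped.* This is true only if dates alone are compared; the flag as written names date and time.
- *That events cluster on Day 42 because patients are examined then.* Protocol Section 7.2.13 schedules the C-SSRS, concomitant medications, AE review and a targeted examination if applicable, but no laboratory tests, ECG or vital signs. The C-SSRS version used covers the period since the last visit. The flag works on onset, so events reported on Day 42 that began earlier are kept. The visit itself may also fall anywhere from Day 40 to Day 44.
- *That the table of TEAEs leading to discontinuation is affected for completers.* Protocol Section 5.3 treats a patient as having completed the study on completing the End of Study visit, so an event beginning at that visit can hardly lead to discontinuation.
- *That about 75% of patients are exposed, from the 25% drop-out assumption.* The rule applies to early terminators as well.
- *That the relative risks are certainly affected.* The text of SAP Section 5.13.1 describes any AE during the study, whereas the title of Table 14.3.1.3 says treatment-emergent. The documents leave this open.

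**Conclusion.** The contradiction is real and undeclared. The SAP flag excludes some or all of calendar day +14 after the last dose, which the protocol counts as treatment-emergent. For completers the effect is confined to onsets on Day 42. It is at most 1 of 42 window days, and about 50% to 71% of that one day if times are compared and dosing falls between 07:00 and 12:00 (an assumption). The number of events affected cannot be derived from the documents and is probably small. Nothing shows an intent to narrow the window; the SAP's stated conformity with the protocol and the silence of Section 8 point to a drafting slip. It is a minor correction, but worth making, because the flag can undercount events against the protocol's own definition.

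**What to change.** In SAP Section 5.13.1, define the flag as onset on or after the first dose, and onset date on or before the calendar date of the last dose + 14 days. Compare dates only at the upper end, so that missing onset times do not matter there. Day 42 onsets in completers then count and Day 43 onsets do not, which matches Protocol Section 10.4.5.2 and the SAP's definition sentence.

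The cost is one clause in the SAP and one comparison in the program. TEAE counts may rise slightly. No entry in Section 8 is needed, since the change removes a departure from the protocol.

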### 5.13.2 Laboratory Data

Descriptive statistics of the observed values and change from baseline (continuous data) will be presented by treatment group and visit for each hematology, urinalysis, chemistry, coagulation, and hormone (ACTH, TSH, cortisol) parameter. Each measurement (continuous data) will be classed as below, within, or above normal range, based on ranges supplied by the laboratory used. Shift tables in relation to the normal range from baseline to each follow-up visit will be presented.

A summary of the number of abnormal parameter values will also be provided. All laboratory data will be listed, with a separate listing only including abnormal (i.e. out of range) values.

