10.4.5.6 Clinical Laboratory Tests

Mean changes from Baseline at each post-Baseline time point for each laboratory variable will be presented. In addition, each reading will be classified as below, within, or above normal range, based on ranges supplied by the laboratory used. Shift tables for the Baseline and follow-up measurements will be presented.

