14.3.2	Listings of Deaths, Other Serious and Significant Adverse Events		
14.3.2.1	Deaths – Safety Analysis Set	IP	
14.3.2.2	Serious Adverse Events – Safety Analysis Set	IP	
14.3.3	Narratives of Deaths, Other Serious and Certain Other Significant Adverse Events		
14.3.4	Abnormal Laboratory Values		
14.3.4	Abnormal Laboratory Values – Safety Analysis Set	IP	
14.3.5	Extent of Exposure, Dosage Information, And Compliance		
14.3.5.1	Treatment Exposure – Safety Analysis Set	IP	
14.3.5.2	Treatment Compliance – Safety Analysis Set	IP	
14.3.6	Vital Signs and Physical Examination		
14.3.6.1	Vital Signs – Safety Analysis Set	IP	
14.3.6.2	BMI and Waist Circumference – Safety Analysis Set	IP	14.3.6.1

Table Number	Table Title	Validation Method	Shell Number (if repeat)
14.3.6.3	Incidence of Orthostatic Hypotension – Safety Analysis Set	IP	
14.3.6.4	Physical Examination – Safety Analysis Set	IP	
14.3.6.5	Shift Table of Physical Examination to Day 28 – Safety Analysis Set	IP	
14.3.7	Other Safety		
14.3.7.1	Hematology – Safety Analysis Set	IP	14.3.6.1
14.3.7.2	Shift Table of Hematology – Safety Analysis Set	IP	
14.3.7.3	Chemistry – Safety Analysis Set	IP	14.3.6.1
14.3.7.4	Shift Table of Chemistry – Safety Analysis Set	IP	14.3.7.2
14.3.7.5	Urinalysis – Safety Analysis Set	IP	
14.3.7.6	Coagulation – Safety Analysis Set	IP	14.3.6.1
14.3.7.7	Hormones – Safety Analysis Set	IP	14.3.6.1
14.3.7.8	12-Lead ECG – Safety Analysis Set	IP	
14.3.7.9	Shift Table of 12-Lead ECG – Safety Analysis Set	IP	
14.3.7.10	Columbia – Suicidal Severity Rating Scale (C-SSRS) – Safety Analysis Set	IP	
14.3.7.11	Summary of Simpson-Angus Scale (SAS) Total Score – Safety Analysis Set	IP	
14.3.7.12	Summary of Abnormal Involuntary Movement Scale (AIMS) Total Score – Safety Analysis Set	IP	14.3.7.11
14.3.7.13	Summary of Barnes Akathisia Rating Scale (BARS) Global Score – Safety Analysis Set	IP	14.3.7.11
14.3.8	Concomitant Medication		
14.3.8	Concomitant Medications by ATC Level 2 and Preferred Name – Safety Analysis Set	IP	14.1.3.3
14.4	PK Tables		
14.4.1	Serum Concentrations, Descriptive Statistics – Pharmacokinetic Analysis Set	IP	
14.4.2	PK Parameters, Descriptive Statistics – Pharmacokinetic Analysis Set	IP	
14.4.3	Dose-Proportionality, Power Model Analysis – Pharmacokinetic Analysis Set	Stat IP	
14.5	PD Tables		
14.6	Other Data		

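### The abnormal-laboratory summary counts out-of-range values without regard to baseline status, which dilutes differences between arms in new abnormalities, and the output list omits shift tables that the text promises

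*SAP*

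**What the plan says.** SAP 5.13.2 plans descriptive statistics "for each hematology, urinalysis, chemistry, coagulation, and hormone (ACTH, TSH, cortisol) parameter". Each continuous measurement is classed as below, within or above the laboratory's range, and "Shift tables in relation to the normal range from baseline to each follow-up visit will be presented". It then adds: "A summary of the number of abnormal parameter values will also be provided". The listing clause of the same section shows that abnormal means outside the range: "with a separate listing only including abnormal (i.e. out of range) values".

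Protocol 10.4.5.6 makes the same promise without limiting it to a laboratory class: "Shift tables for the Baseline and follow-up measurements will be presented".

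SAP Section 10 carries the count as Table 14.3.4, titled "Abnormal Laboratory Values". It lists two laboratory shift tables: 14.3.7.2 ("Shift Table of Hematology – Safety Analysis Set") and 14.3.7.4 ("Shift Table of Chemistry"). Urinalysis (14.3.7.5), coagulation (14.3.7.6) and hormones (14.3.7.7) each have one table and no listed shift table.

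**The concern.** A safety reader wants to know from an abnormality table how many patients in each arm became abnormal on treatment. A count of values does not answer that. A patient who was out of range before the first dose adds to the count in the same way as one who became abnormal on drug, and adds to it in every arm alike. A real excess of new abnormalities on LB-102 is then measured against a background unrelated to treatment. Where an analyte is measured repeatedly, one persistent abnormality also counts several times, and an early leaver contributes fewer values than a completer.

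The SAP does otherwise elsewhere. Adverse events (5.13.1) are counted once per patient and term, with number and percent of patients, and orthostatic hypotension (5.13.3) is summarized as a number of patients.

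Shift tables would supply the missing information on baseline status, so it matters that the output list contains fewer of them than the text promises.

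**Working it through.** The plan states no figure on this point, so there is none to reproduce. The check has two parts.

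**1. Text against output list and schedule**

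Visits are from the Schedule of Assessments in Protocol 7.1.

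| Class | Scheduled pre-dose | Scheduled post-baseline | Shift table in SAP Section 10 |
|---|---|---|---|
| Hematology | Screening, Day 1 | Days 8, 15, 21, 28/ET (4) | Yes |
| Chemistry, with prolactin | Screening, Day 1 | Days 8, 15, 21, 28/ET (4) | Yes |
| Urinalysis | Screening, Day 1 | Days 8, 15, 21, 28/ET (4) | No |
| PT, aPTT, INR | Screening, Day 1 | Day 28/ET (1) | No |
| TSH | Screening | Day 28/ET (1) | No |
| ACTH, cortisol | Day 1 | Day 28/ET (1) | No |

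Shift tables are listed for two of the five classes named in 5.13.2. A persistent abnormality can count four times post-baseline in the first three rows, or six times if pre-dose values are included. It counts once post-baseline in the last three.

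**2. Illustrative dilution**

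All rates here are assumptions. Let p be the proportion abnormal at baseline, taken as persistent; q the proportion of the rest who become abnormal (5% placebo, 10% LB-102); V the number of post-baseline visits; and m the mean number of abnormal values per new case. If a new abnormality starts at a random visit and persists, m = (4+3+2+1)/4 = 2.5 for V = 4, and m = 1 for V = 1.

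Abnormal values per patient = pV + (1−p)qm. The ratio of arms is this expression at q = 0.10 divided by its value at q = 0.05.

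Four visits, post-dose values only:
- p = 2%: (0.08 + 0.245)/(0.08 + 0.1225) = 1.60
- p = 5%: (0.20 + 0.2375)/(0.20 + 0.11875) = 1.37
- p = 10%: (0.40 + 0.225)/(0.40 + 0.1125) = 1.22
- p = 20%: (0.80 + 0.20)/(0.80 + 0.10) = 1.11

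Simulating the planned 25% drop-out, with leavers attending one to three of the four visits, moves these ratios by at most about 0.03.

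One visit (coagulation, hormones), where a post-baseline count of values is a count of patients:
- p = 10%: (0.10 + 0.09)/(0.10 + 0.045) = 1.31
- p = 20%: (0.20 + 0.08)/(0.20 + 0.04) = 1.17

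Among patients not abnormal at baseline, the ratio is 0.10/0.05 = 2.0 in every case. At p = 10%, ignoring baseline status takes 2.0 down to 1.31, and repeat counting takes it on to 1.22. The missing baseline condition does most of the harm.

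The share of post-baseline abnormal values that comes from pre-existing cases is pV/(pV + (1−p)qm). With V = 4:
- p = 2%, q = 30%, m = 4: 0.08/(0.08 + 1.176) = 6%
- p = 20%, q = 2%, m = 1: 0.80/(0.80 + 0.016) = 98%

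These are the extremes over p = 2–20%, q = 2–30% and m = 1–4.

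**The case against.** The strongest case on the other side has five parts.

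- **The two defects barely overlap.** Repeat counting affects hematology, chemistry and urinalysis, and the first two have listed shift tables that show patients by baseline status. Prolactin, the laboratory signal expected from Phase 1, is among the chemistry tests. This stands, and it reduces the point. Urinalysis alone has both problems. Even so, the shift tables run visit by visit and do not give patients with any new abnormality during treatment.
- **Pre-existing abnormalities need not dominate the table.** A reader might infer that they do. The documents do not support it: they give no rates, and the share runs from 6% to 98% over plausible assumptions. Only dilution is established.
- **Coagulation and hormones are not without planned shift tables.** That too is a tempting inference. The SAP and protocol texts promise shift tables with no class excluded, so what is shown is a mismatch with Section 10.
- **The table shell is not available.** It might present counts by visit. SAP 5.3 also provides for percentages with patient denominators, so the unequal 3:3:3:1 allocation alone does not show that the arms cannot be compared. This is fair as to layout, but the governing sentence names values as the unit and mentions no baseline status.
- **New abnormalities also reach the adverse event tables.** Protocol 9.1.4 requires this when they need intervention or tests, lead to discontinuation, come with symptoms or signs, or are judged clinically significant. That route depends on clinical consequence or judgement. It does not replace a count based on the laboratory range.

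**Conclusion.** The point holds as a minor improvement to descriptive safety reporting. As worded, the summary mixes new and pre-existing abnormalities and understates a relative difference between arms in new ones. Under the assumed 5% versus 10% with four visits, a doubling shows as about 1.6 at 2% baseline prevalence and about 1.2 at 10%. These figures rest on assumed rates, on full persistence of baseline abnormalities and on new abnormalities lasting once they start. Lower baseline prevalence reduces the effect. For coagulation, TSH, ACTH and cortisol, only the lack of a baseline condition applies post-dose.

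The mismatch between the shift tables promised and those listed is established from the text alone. No hypothesis test or efficacy result depends on either matter.

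**What to change.** - **Table 14.3.4 and SAP 5.13.2.** Replace the count of values with n/N (%) of patients, by parameter and direction (low, high). N is the patients with a Baseline value not abnormal in that direction and at least one post-baseline value; n is those among them with at least one post-baseline value out of range in that direction. State whether unscheduled and repeat values count, since SAP 5.2.17 leaves them out of tabulations by default. Worsening in patients already out of range would still be seen through the planned change-from-baseline summaries and listings.
- **SAP Section 10.** Add shift tables for coagulation, hormones and the continuous urinalysis parameters, to match 5.13.2 and Protocol 10.4.5.6.

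The cost is a few lines of SAP text, shell changes and modest programming. All the data are already collected.
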